- the study involves a test article being administered or dispensed to subjects NOT according to a clinician's medical judgment but rather, per the study protocol, OR
- the study does not involve a test article but intends to provide safety or efficacy data to the FDA.

Yes

No

2. * Indicate the FDA regulated product(s) this study involves:

Drug

**Medical Device**

Biologic

Dietary Supplement

Food/Food Additive

Color Additive

Electronic Products for Human Use (radiation producing)

Other

3. * Is this study supported by the Department of Defense (DoD):

Yes

**No**

4. * Check if any of the following funding sources apply to this research (including Direct and/or Indirect funding):

Department of Education

Department of Justice

Environmental Protection Agency

**None of the above**

ID: HM20022338

View: SF2 - IRB Panel Setup

IRB Panel Setup

1. * To which IRB is this study being submitted for review?

- VCU IRB
- WCG IRB
- NCI Central IRB
- Advarra IRB
- Other IRB

2. * Is this study transitioning to review by another IRB?

- Yes - transitioning from VCU IRB to an external IRB (WCG, CIRB, Other)
- Yes - transitioning from an external IRB (WCG, CIRB, Other) to VCU IRB
- No or not applicable

ID: HM20022338

View: SF2 - Review Setup

Review Setup

1. * Select which study type best describes the majority of the study. Your response will help determine which IRB panel should review this.

- Bio-Medical Research
- Social/Behavioral/Education (SBE) Research

2. * Which option(s) best describe the way(s) this study's procedures will be conducted? (Select all that apply.) This information may be used by the IRB in triaging studies during an emergency.

- In-person interactions / interventions with participants
- Remote interactions / interventions with participants
- Secondary data/specimen analyses and no contact with study participants

3. * Would it be possible to convert in-person activities in your study to remote if there is an approved contingency protocol?

No, not possible to convert to remote activities

4. * Does this study involve greater than minimal risk:

- Yes No

5. * Review type requested: (subject to IRB approval):

- Full Board
- Expedited
- Exempt

The IRB has determined that the selected types of anticipated individual and social benefit apply to this study

The below information is read-only to investigators, and the categories are set by the IRB during review. All categories will appear blank until the IRB has made a determination. If a category is not checked, it does not apply to this study. This information may be used by the IRB in triaging studies during an emergency situation.

Possible or minimal direct benefit to individual participants

ID: HM20022338

View: SF2 - Initial Setup Complete

Initial Setup Complete

Protocol Progress:

? **INITIAL SETUP**

? BACKGROUND, RATIONALE & GOALS

? RESEARCH PLAN

? CONSENT PLAN

? RISKS, PRIVACY & CONFIDENTIALITY

? POPULATIONS WITH SPECIAL CONSIDERATIONS

? INSTITUTIONAL REQUIREMENTS

? DOCUMENTS

Click Continue below to go to the next section

ID: HM20022338

View: SF2 - Background, Rationale and Goals

Background, Rationale and Goals

- * Describe the study's background and what is currently known from the scientific literature, including citations, or upload a citation list in document upload. Use lay language whenever possible.**

Anesthesiology has been at the forefront of patient safety in the perioperative setting for many years, including the introduction of innovations in patient monitoring and airway management. The risk involved in anesthesiology remains significant, and multifold, with adverse outcomes ranging from death, to nerve injury, airway complications, and emotional distress. In fact, in the Anesthesia Closed Claims database, from 2005 to 2014, reflected that for the 1,567 claims pertaining to adverse events resulting in patient injury, death accounted for 30%, nerve damage 21%, brain injury 9%, and airway injury 7%. Furthermore, the most common damaging events in perioperative anesthesia care were respiratory (22%) and equipment (20%) events.

The Anesthesia Closed Claims database project further examined the rapidly expanding role of non-operating room anesthesia (NORA). These scenarios represent a burgeoning expansion of anesthesia care, where anesthesia providers are asked to provide primarily sedation in a range of areas, including gastroenterology endoscopy suites, radiology care suites, and many other locations. The pattern of injury in NORA claims was similar in distribution to claims arising in the OR; however, death and permanent brain damage made up a greater percentage (68%) of NORA claims than OR claims (39%). Most of the claims were related to oversedation with respiratory depression, and one third of the cases were judged to have likely been preventable with better respiratory monitoring. This applied particularly to continuous end-tidal CO₂ monitoring, which was used in only 15% of the claims associated with oversedation.

The prevention of injuries ultimately demands situational awareness from individual practitioners and cognitive, nontechnical, and technical skills to address a potentially dangerous clinical scenario before an injury occurs. This has proven challenging given the number of distractions that may be present in the operating room. Maintaining a stable airway in a sedated patient undergoing monitored anesthesia care (MAC) is a critically important aspect of providing a safe anesthetic. Failure to maintain a patent airway and avoid its obstruction results in impaired ventilation. Without correction, this leads to oxygen desaturation, hypoxemia, resulting in potentially devastating cardiac arrest, that may lead to death or anoxic brain injury.

Monitoring arterial oxygen saturation is typically done with peripheral pulse oximetry (SpO₂), a non-invasive method of measuring oxygen saturation in red blood cells in the arterial circulation. This is considered a standard monitor by the American Society of Anesthesiologists and usually takes the form of sticker that is placed on a finger, ear lobe, nostril, or forehead during anesthetics and throughout the hospital setting. This is helpful in determining if oxygen desaturation is occurring during anesthesia and sedation, perioperatively. Airway obstruction due to the anesthesia-induced suppression of upper airway reflexes is not uncommon during MAC. The upper airway reflexes consist of many different types of reflex responses such as sneezing, apnea, swallowing, laryngeal closure, coughing, expiration reflex, and negative pressure reflex. Although the activation of upper airway reflexes does not necessarily occur at one particular site of the respiratory tract, individual reflex response is usually considered to be highly specific for the particular respiratory site which has been affected. The upper airway reflexes are modified by many factors such as sleep, anesthesia, and background chemical ventilatory drive. Both depression and exaggeration of upper airway reflexes cause clinical problems. Depression of upper airway reflexes enhances the chance of pulmonary aspiration and compromises the maintenance of the airway, whereas exaggeration of airway reflexes such as laryngospasm and prolonged paroxysm of cough can be harmful and dangerous.

End-tidal CO₂ (ETCO₂) has been used in multiple studies as a monitor of respiratory suppression. MAC is usually done with multiple bolus doses of sedation, or a continuous infusion of anesthetic, which can result in respiratory suppression. For this reason, monitoring of ETCO₂ has commonly been used as a surrogate for unobstructed and adequate ventilation, i.e. air exchange. In the case of MAC, the breathing system is not closed as it is with an endotracheal tube used in general anesthesia (GA). As such, the value of ETCO₂ recorded may not be exactly accurate due to escape of ETCO₂ to the environment. Nonetheless, the presence of a capnography waveform is reassuring and is routinely used in our healthcare system as a surrogate for ventilation during MAC, as several studies have shown ETCO₂ to accurately detect airway obstruction.

When airway obstruction does occur during MAC, anesthesia providers often are able to place a patient in the sniffing position. This position aligns the airway in such a way as to minimize obstruction caused by the relaxation of the tongue and upper airway reflexes during anesthesia. If this cannot be achieved stably and safely, the decision is made to convert the anesthesia to GA. The incidence of this is typically low, but involves higher risk, as airway intervention in the way of intubation with an endotracheal tube to facilitate mechanical ventilation is needed, as well as establishment of a deeper plane of anesthesia with medications that can result in hypotension and other medication-related complications.

The Stable Airway Management (SAM) device is designed to maintain the sniffing position effectively and prevent the patient from sliding back into an obstructed airway position. This can reduce the incidence of apnea, which can result in oxygen desaturation if not treated quickly by an attentive anesthesia provider. One study found the incidence of apnea (defined as > 20 seconds) during MAC to be as high as 26%, and a subsequent study by the same group found the incidence to be even higher, 49.5% of 99 patients demonstrating > 60 seconds apnea during MAC sedation cases. Doing this effectively would alleviate the need for frequent airway manipulation during the procedure, which risks awakening the patient, disrupting the procedure, and takes attention away from monitoring the other complex aspects of anesthetic care.

The importance of the study lies in the knowledge of whether the SAM can be safely used in adult patients undergoing MAC in the supine position. Furthermore, we plan to examine if its use can help reduce the incidence of airway obstruction and consequently apnea, which has significant risk, including oxygen desaturation and impaired ventilation, which can result in severe hypoxemia and even death. This could provide significant improvement in safety in anesthesia care.

5. * Describe any potential for direct benefits to participants in this study:

Potential direct benefits to study participants include airway stability during MAC that reduces the risk for airway obstruction and apnea, and therefore need for manipulation of the airway or interruption of their stable anesthetic.

6. * Describe any potential for direct social impact in this study . For example, any engagement with specific communities to respond to community-identified needs, or ways the study will strengthen the well-being of the specific communities if applicable:

If proven successful, utilization of the SAM will provide an increased margin of safety for patients during monitored anesthesia care cases, allowing for faster procedure times and decreased medical costs.

7. Upload a supporting citation list if applicable:

ID: HM20022338

View: SF2 - Study Population

Study Population

1. * Provide the maximum number of individuals that

1. May participate in any study interaction or intervention (Including screening, consenting, and study activities)

AND/OR

2. You obtain any data/specimens about (regardless of identifiability)

at VCU and at other sites under the VCU IRB's oversight. See the help text for additional guidance.

40

2. If this is a multi-Center Project, what is the maximum anticipated number of subjects across all sites?

This will be a single-center project conducted at VCU.

3. * Provide justification for the sample size by explaining how you arrived at the expected number of participants and why this number is adequate for answering the research questions:

The overarching goal of this pilot treatment study is to obtain estimates of the means and variances of all study measures to calculate effect sizes to facilitate a power analysis for future extramurally funded clinical trials. The method of setting the pilot trial sample size in order to minimize the overall sample size of a pilot and main trial together was described by Kieser and Wassamer. They applied an 80% upper confidence limit approach to the sample size calculation and found that a pilot trial sample size between 20 and 40 would minimize the overall sample size for a main study sample size of 80-250, corresponding to standardized effect sizes of 0.4 and 0.7, for 90% power based on a standard sample size calculation. We will employ the same approach here. Two randomized groups will be examined, Standard of Care versus SAM deployment. Each group will have an n=20. In total, there will be 40 total participants, where 20 participants receive the standard of care, and 20 receive SAM deployment.

4. * List the study inclusion criteria:

1. Patients undergoing MAC anesthesia in the supine position
2. patients able to give informed consent

5. * List the study exclusion criteria:

1. Age < 18 years
2. Non-elective procedures
3. Surgery duration > 180 minutes
4. Presence of a cervical spine injury, instability, or cervical spine collar
5. Patients with airway, facial, or other anatomy deemed inappropriate for SAM use by anesthesiologist
6. General anesthesia as primary anesthetic
7. Prisoners
8. Pregnant women

Vulnerable subjects: No vulnerable patient populations will be enrolled in this study.

6. * Will individuals with limited English proficiency be included in or excluded from this research?

Included

- Excluded - safety concerns if participants are unable to communicate with the study team
- Excluded - instruments/measures only validated in English
- Excluded - no prospect of direct benefit to individual participants
- Excluded - minimal risk study
- Excluded - lack of budget/resources for translation and interpretation [provide an explanation in next question]
- Excluded - other reason [provide an explanation in next question]

7. Justify the inclusion and exclusion criteria if you are either targeting, or excluding, a particular segment of the population / community. Provide a description of the group/organization/community and provide a rationale.

The reason for not including pregnant women in this pilot study is because the patient population for this initial study is elective surgical patients, for which most pregnant women are excluded, independent of this study design - pregnant women requiring surgery are almost always urgent/emergent and would not fit criteria for this study.

A cesarean section is in fact many times elective, but MAC is typically not used and the patient is awake, also precluding inclusion in this study.

ID: HM20022338

View: SF2 - Background, Rationale & Goals Section Complete

Background, Rationale & Goals Section Complete

Protocol Progress:

? INITIAL SETUP

? BACKGROUND, RATIONALE & GOALS

? RESEARCH PLAN

? CONSENT PLAN

? RISKS, PRIVACY & CONFIDENTIALITY

? POPULATIONS WITH SPECIAL CONSIDERATIONS

? INSTITUTIONAL REQUIREMENTS

? DOCUMENTS

Click Continue below to go to the next section

ID: HM20022338

View: SF2 - Study Procedures

Study Procedures

1. * Describe the study hypothesis and/or research questions. Use lay language whenever possible.

We hypothesize that the Stable Airway Management device (SAM) will prove safe and result in a 20% lower incidence of apnea compared with standard of care. It is furthermore hypothesized that there will be equal or fewer conversions from monitored anesthesia care (MAC) to general anesthesia for airway-related problems, for patients using the SAM.

2. * Describe the study's specific aims or goals. Use lay language whenever possible.

The goal of the research at hand is to determine if the SAM can be used safely, and as a useful adjunct in anesthesia care.

The specific aims of this study are the following:

1. To study the safety and feasibility of the use for the Stable Airway Management (SAM) device in monitored anesthesia care (MAC) cases.
2. To study the incidence of airway obstruction resulting in apnea during MAC with use of the SAM vs. standard of care.

3. * Choose all types of recruitment materials that may be used and upload them below:

- E-mail invitations
- Phone Solicitation scripts (i.e. cold calls or random-digit-dialing)
- Flyers, Mailed Letters or Newspaper/TV/Radio Ads
- TelegRAM announcements
- Website text
- Study-specific web sites (provide the design and text)
- Social Media
- EPIC MyChart Patient Portal research study descriptions
- Psychology Research Participant Pool (SONA) study descriptions
- Scripts for announcements made to groups
- Other recruitment material
- No recruitment materials**

4. * Describe the study procedures/methods for identifying and recruiting participants. Address the following three aspects of recruitment in your response.

1. Identification of potentially eligible participants or secondary data/specimens of interest.

- What database(s) will be queried to identify secondary data/specimens
- How potential participants' contact information will be obtained

2. Recruitment procedures to invite participation in the study (when applicable):

- How each of the written or verbal recruitment materials and reminders (selected above) will be used
- Who will contact or respond to potential participants
- Locations where recruitment procedures will take place
- The timing and frequency of recruitment attempts

3. Eligibility screening prior to consent and how those activities will be carried out (when applicable)**See the help text for additional guidance.**

Patients undergoing monitored anesthesia care (MAC) cases on the surgical schedule will be identified by the clinical research coordinator (CRC). The CRC will screen for potential participants using the electronic medical record, examining the clinic schedule prior to patients' preoperative clinic appointments, and looking for the expected surgical procedures that would warrant MAC. The patient's name, date of surgery, and date of birth will be collected as part of this CRC screening process. The CRC will consent patients during their preoperative clinic appointment prior to surgery and will ensure that participants do not meet the exclusion criteria prior to consent.

5. * Does this study have a separate protocol document (i.e. a multisite or sponsor's protocol) that contains a detailed description of the study's methodology?

Yes

No

6. * Since a separate protocol document is not uploaded, describe the proposed research using language understandable to those IRB committee members whose expertise is not scientific. The description must include:**1. A statement explaining the study design****2. A detailed description of all the procedures that will be followed to carry out the study, preferably in sequential order, and in sufficient detail that the study's methods could be replicated****3. A description of all research measures/tests/interventions that will be used (if applicable)****See the help text for additional guidance**

This study is a non-blinded, randomized controlled trial in which participants undergoing MAC (monitored anesthesia care) for scheduled surgical procedures will be randomized to two arms, with the research coordinator (CRC) using an electronic randomizer to assign participants into the two study arms.

The study investigators will conduct in-person training sessions with the SAM device for anesthesia staff (anesthesiologists and nurse anesthetists administering anesthetic care) prior to their care of patients who are consented for the study. The CRC will be trained by the investigators in use, deployment, and troubleshooting of the device., and will assist during these sessions. These training sessions will take place prior to the initiation of patient enrollment in the study, and the investigators will be available to help with any questions from anesthesia providers. We will document a list of anesthesia providers who have completed the training, and only these providers will be permitted to use the SAM device for patients enrolled in the study. The CRC and investigators will be readily available to anesthesia providers for any issues that arise during study procedures as well. All procedural care related to the study will be in a standard of care operating room setting in which these surgical procedures routinely take place.

Each arm will undergo standard anesthetic procedures for MAC, which include standard monitoring of blood pressure, SpO2, electrocardiogram monitoring, etCO2 waveform capnography, and the availability of temperature monitoring. The medications used to achieve an adequate MAC anesthetic will be at the discretion of the anesthesia provider, and medications used will be noted. One arm, the intervention arm, will aim for maintenance of a patent airway with the SAM device, while the other will be a standard of care (SOC) arm. In the intervention arm, the anesthesia provider will be given a SAM device that will be used to maintain the patient's head in a slight sniffing position, and adjust as necessary to maintain the desired head position that is optimal for a patent airway, thereby facilitating unobstructed breathing. In the SOC arm, the same goal will be maintained, but with traditional methods, which often include pillows or towels, if anything. If the SAM use becomes unsafe for a given subject, care can be converted to standard of care, at the discretion of the anesthesia provider, and reason for cessation of use will be documented and reviewed by the DSMB. We will measure the number of apneic events, defined as > 20 seconds apnea as detected by capnography, per 15-minute interval and total number per patient, between the two arms, as well as the incidence of conversion from

MAC to general anesthesia for airway-related complications. We will also have anesthesia providers document the number of head/airway manipulations needed per 15-minute intervals.

The safety of the SAM over the course of the study will be determined by comparison to the SOC, specifically regarding number of conversions to general anesthesia for airway-related complications. This data will be reviewed by the DSMB. The safety of continuing to use the SAM during a given procedure for a study participant in the SAM arm will also be at the discretion of the anesthesia provider, specifically looking at repeated oxygen desaturation or inability to maintain the airway with the SAM, that would necessitate use of a different airway management tool.

7. * The IRB only reviews research activities, so indicate which of the study activities are:

- Being performed exclusively for research purposes (i.e. they would not otherwise be done apart from this study) **VERSUS.**

- Alterations of routine activities/procedures (e.g. the study is altering the timing, frequency, method, location, amount, etc.) **VERSUS.**

- Being done for other purposes and whose data/results will be used secondarily in the study (e.g. standard medical or psychological tests, routine education practices, quality improvement initiatives, etc.).

All study activities are being performed exclusively for research purposes.

8. If applicable, describe alternatives (research or non-research) that are available to potential participants if they choose not to participate in this study:

If potential participants choose not to participate in this study, they will undergo their scheduled surgical procedure and not be enrolled in the study.

9. Upload any supporting tables or documents (e.g. protocol documents, figures/tables, data collection forms, study communications/reminders):

Upload **ALL** instruments/guides that will be used or that participants will experience (i.e. see, hear, complete), including measures, scripts/questions to guide interviews, surveys, questionnaires, observational guides, etc.:

Upload **ALL** recruitment and screening materials, including such as ads, flyers, telephone or in-person scripts, letters, email invitations, TelegRAM announcements, and postcard reminders, screening scripts, screening forms, and screening measures:

ID: HM20022338

View: SF2 - Project Details

Project Details

1. * Select all of the following types of interventions that apply to this study (selections will branch):

- Social/Behavioral interventions or experimentation / Tasks / Environmental manipulations
- Deception (misleading participants through false or incomplete information)
- Drug(s) / Biologics / Supplement(s) / Other Compounds (investigational products or products whose administration is dictated by the study protocol and not per the physician's clinical judgment)
- Placebos
- Safety and/or effectiveness evaluation of Bio-Medical Device(s), including in-vitro diagnostic devices/assays, mobile medical apps, and HUDs used in clinical investigations**
- Washout Periods
- Expanded Access - Treatment Use of an Investigational Product
- Medical or Surgical Procedures (eg: physical exam, clinical procedures, scans, etc)
- Specimen/biological sample collection
- None of the Above

2. * Select all of the following types of interactions that apply to this study (selections will branch):

- Surveys / Questionnaires /Written responses to questions (including data entry)
- Active Internet data collection (i.e. using the internet to interact or intervene directly with research participants)
- Interviews / Focus Groups / Verbal responses to questions
- Audio / Video recording or photographing participants
- Observations
- Passive Internet data collection (i.e. passively observing online behavior)
- Educational Settings/Assessments/Procedures
- None of the Above**

**3. * Select all types of secondary information and/or specimens that apply to this study (selections will branch):
See the help text for definitions.**

- Individually Identifiable Health Information (PHI or RHI)**
- Secondary data/specimens NOT from a research registry or repository
- Information/specimens from a research registry or repository (Usage Protocol)
- Information/specimens originally collected for a previous research study
- Publicly available information/specimens
- Government-generated or collected information that was or will be obtained for nonresearch activities [only applicable to research conducted by or on behalf of a Federal department or agency]
- No secondary data/specimens will be used

ID: HM20022338

View: SF2 - Bio-Medical Device Details

Bio-Medical Device Details

1. * Select the type of device :

- Marketed Device (including 510k device) used as indicated
- Marketed but new indication or intended use
- Mobile application with regulatory discretion
- Mobile application without regulatory discretion
- Investigational device**
- Humanitarian Use Device (HUD)

2. * List devices this study will involve:

Device	Manufacturer	Device Risk	IDE	IDE Holder
Stable Airway Management	Atlantic Wave LLC	Non-Significant Risk	Abbreviated IDE	Not Required

3. * Describe how the device will be stored and controlled.

All Stable Airway Management (SAM) devices will be controlled by the clinical research coordinator and stored in their office.

4. **A. For each device listed above, upload documentation of the approved use(s) (operation manual, instructions for use, etc.) or a detailed description of the design, use, and risks of the device.**

B1. If 'Investigational Medical Device' or 'New Use for Marketed Medical Device' was selected above AND the device qualifies for IDE exemption under under 21 CFR 812.2(c), upload one of the following documents for each applicable device:

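### SAM's safety is judged between arms on conversions to general anesthesia alone, so an excess of oxygen desaturation without a 20-second apnea could go uncompared although SpO2 is monitored in both arms

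*Protocol*

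**What the plan says.** The protocol's case for the trial runs through oxygenation. Background, Rationale and Goals, item 1, says of impaired ventilation: "Without correction, this leads to oxygen desaturation, hypoxemia, resulting in potentially devastating cardiac arrest, that may lead to death or anoxic brain injury". Item 4 of the same section gives apnea its importance in the same terms: "which has significant risk, including oxygen desaturation and impaired ventilation, which can result in severe hypoxemia and even death". Specific aim 1 is safety and feasibility.

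Study Procedures, item 6, then fixes what is done:

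- **Monitoring:** "Each arm will undergo standard anesthetic procedures for MAC, which include standard monitoring of blood pressure, SpO2, electrocardiogram monitoring", together with capnography.
- **Apnea:** "We will measure the number of apneic events, defined as > 20 seconds apnea as detected by capnography, per 15-minute interval", and in total per patient, compared between arms.
- **Conversions:** the same sentence adds "as well as the incidence of conversion from" MAC to general anesthesia because of airway complications.
- **Manipulations:** providers chart head and airway manipulations by 15-minute interval.
- **Study-level safety:** SAM is compared with standard of care on the number of those conversions, and the DSMB reviews this.
- **Patient-level safety:** whether to go on using SAM is left to the provider, "specifically looking at repeated oxygen desaturation or inability to maintain the airway with the SAM". A patient may be moved to standard of care, with the reason documented for the DSMB.

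Under Risks, Discomforts, Potential Harms and Monitoring, the stopping trigger concerns jaw or neck pain in 20% of SAM patients. The DSMB meets monthly and reviews unblinded compliance and adverse events. Desaturation is not named there.

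**The concern.** The protocol names desaturation as the route from a lost airway to death or brain injury and watches for it in every patient, but leaves it out of the comparison that decides whether the device is safe. The event it does compare is one that Background item 1 describes as infrequent, and it is a clinical decision made in an unblinded trial.

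There is also a way out of the count. A SAM patient who desaturates can be returned to standard of care. That step is not a conversion to general anesthesia, so unless a conversion follows, the event does not enter the study-level safety comparison.

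At stake is the conclusion on aim 1. More frequent or deeper desaturation under SAM, managed at the bedside without general anesthesia, would leave the stated criterion satisfied. A later trial would be planned on that result.

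**Working it through.** **Step 1: where desaturation could be seen.** The protocol gives no figure to reproduce, so the first check is a reading of each channel.

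| Channel | Both arms? | Captures desaturation? |
|---|---|---|
| Conversions to general anesthesia | Yes | Only if it ends in conversion |
| Apnea over 20 s on capnography | Yes | Only when such an apnea accompanies it |
| Head/airway manipulations | Yes | Not directly |
| Reason for stopping SAM | SAM arm only | Yes, if it is the reason given |
| Adverse events to the DSMB | Not restricted to one arm | Only if reported as such; no definition |
| Jaw/neck pain trigger | SAM arm only | No |

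No row gives a defined SpO2 measure compared between arms.

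**Step 2: how much the conversion count can show.** Inputs: 20 patients per arm (Study Population, item 3) and the hypothesis of equal or fewer conversions with SAM. The protocol states no conversion rate, so 1%, 2% and 5% in the standard arm are assumptions.

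- No conversion in 40 patients, same rate p in both arms: (1 − p)^40. This gives 0.99^40 = 0.669, 0.98^40 = 0.446 and 0.95^40 = 0.129.
- Chance of observing equal or fewer conversions with SAM: the sum over i of P(X_SAM = i) × P(X_SOC ≥ i), with both counts binomial, n = 20.

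| Assumed standard-arm rate | SAM rate equal | SAM rate doubled | SAM rate tripled |
|---|---|---|---|
| 1% | 0.848 | 0.718 | 0.607 |
| 2% | 0.761 | 0.573 | 0.427 |
| 5% | 0.655 | 0.386 | 0.209 |

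- If 0 of 20 SAM patients convert, the exact two-sided 95% upper limit is 1 − 0.025^(1/20) = 0.168.

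So even for conversions themselves, the hypothesized result is likely at the lower assumed rates when SAM truly doubles the risk.

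**Step 3: what a desaturation comparison would offer.** The proportions with at least one desaturation are also assumed. Approximate 95% interval: difference ± 1.96 × √(p1(1 − p1)/20 + p2(1 − p2)/20).

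- Standard 10%, SAM 30%: 0.20 ± 1.96 × √(0.0045 + 0.0105) = 0.20 ± 0.24, or −4 to +44 points. Power is 35%. The chance that SAM shows the higher count is 0.925.
- Standard 20%, SAM 40%: 0.20 ± 1.96 × √(0.008 + 0.012) = 0.20 ± 0.277, or −8 to +48 points. Power is 28%. The chance that SAM shows the higher count is 0.892.

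The direction of an excess this large would usually be visible, but a formal test would usually miss it.

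**The case against.** The best defense is that apnea already does this work. Apnea over 20 seconds on capnography is monitor-based, has a fixed definition, lies upstream of desaturation and is compared between arms. If SAM worsened obstruction to the point of apnea, the trial would show it. This stands, and it limits the point to desaturation without a 20-second apnea, for example from partial obstruction or hypoventilation.

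A reader might go further and infer that capnography is unreliable here, leaving SpO2 as the only objective measure. The protocol does not support that. Its open-system caveat concerns the recorded ETCO2 value, and the same paragraph defends the waveform and its ability to detect obstruction.

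A reader might also infer that desaturation goes wholly unrecorded. It does not: cessation reasons are documented for the DSMB, and the DSMB sees adverse events. But cessation reasons exist in one arm only, and desaturation is not defined as an adverse event, so neither supplies a comparison.

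Two practical objections also stand. The protocol says SpO2 is monitored, not that a continuous record is stored. And because the trial is unblinded, provider responses such as supplemental oxygen could affect SpO2 differently by arm.

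That details may sit in a statistical analysis plan does not settle the matter. The protocol itself fixes both the list of measures and the safety criterion.

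**Conclusion.** The point holds in a limited form. The study-level safety criterion rests on conversions alone, and desaturation is not compared between arms, so SAM could produce more desaturation without 20-second apneas and still meet the criterion. That follows from the text and needs no assumed rate.

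The sizes do rest on assumptions. At conversion rates of 1% to 5% in both arms, 67% to 13% of trials would have no conversion at all. If SAM doubled those rates, the result would still be equal or fewer conversions in 72% to 39% of trials.

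It would be too strong to say that zero conversions tell nothing. 0 of 20 still bounds the SAM rate at 16.8%, which is weak information but not none. Nor would adding SpO2 turn a 40-patient pilot into a test of safety. It would supply a descriptive estimate, which suits the pilot's stated purpose of estimating means and variances. The change is worth making before enrolment.

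**What to change.** In Study Procedures, item 6, add SpO2 as a descriptive comparative safety outcome beside conversions:

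- Record it in both arms from standard monitoring: lowest SpO2, number of desaturations and minutes below one threshold, per patient. The investigators fix the threshold before enrolment.
- Report it by randomized arm, keeping patients taken off SAM in the SAM arm, with estimates and confidence intervals.
- Note supplemental oxygen use so the values can be interpreted.
- Give the by-arm summary to the DSMB.

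The bedside decision rule and the sample size stay as they are.

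The cost is protocol wording, some artefact cleaning and the oxygen note. Availability of a stored SpO2 record must be confirmed first. If there is none, SpO2 can be charted at the 15-minute intervals already used for the other measures, which would be coarser for lowest values and durations. With 20 per arm the comparison should be labelled descriptive.
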